STUDY PROTOCOL & STATISTICAL ANALYSIS PLAN

Official Title:	HYPERTHERMIA AS AN ADDITIONAL TREATMENT FOR THE BIOLOGY AND EXPERIENCE OF DEPRESSION: THE HEATBED STUDY
Clinicaltrials.gov #	NCT05708976
Date	25 September 2025
Development Phase:	Feasibility & Acceptability
Sponsor:	[name] & [name] UCSF Osher Center for Integrative Health School of Medicine [name]
Principal Investigator:	Name: [name] E-mail: [contact]
Co-Principal Investigator	Name: [name] E-mail: [contact]

BACKGROUND

Depression recovery is not uniformly linear; people who recover from depression often experience acute improvements, termed ‘sudden gains,’ early in treatment. Data suggest that participants with clinical depression who receive whole body heating (Hanusch et al., 2013; Janssen et al., 2016) and participants who receive cognitive behavioral therapy (CBT) treatment (Aderka et al., 2012; Tang et al., 1999) show sudden gains. Ascertaining if a treatment comprising both sauna sessions and CBT sessions is feasible and tolerable will allow for further research of this integrative mind-body treatment as a potentially effective and disseminable treatment for clinical depression.

Prior work has demonstrated that whole body heating to an internal temperature of 38.5 °C (101.3 °F) using a head out infrared heating device is tolerable by healthy adults and is associated with significant reductions in clinical depression (Hanusch et al., 2013; Janssen et al., 2016) that characterize sudden gains. This prior work administered a single sauna session in a Heckel heating device, a medical hyperthermia device, and reported improvements in depression symptoms within 1 week of this session. This prior work did not ascertain if additional sauna sessions led to further decreases in depression; a dose-escalation study has not yet been performed. Our earlier pilot project established (in $N=25$ participants) that a readily accessible, commercially available sauna, which the UCSF IRB granted NSR designation, can achieve a core temperature of 101.3 °F without serious adverse events.

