TITLE	EXAMINING THE FEASIBILITY AND ACCEPTABILITY OF SAUNA SESSIONS AND COGNITIVE BEHAVIORAL THERAPY (CBT) FOR PARTICIPANTS WITH CLINICAL DEPRESSION
SPONSOR	[name]
CO-SPONSOR	[name]
NUMBER OF SITES	1
RATIONALE	Depression recovery is not uniformly linear; people who recover from depression often experience acute improvements, termed ‘sudden gains,’ early in treatment. Data suggest that participants with clinical depression who receive whole body heating (Hanusch et al., 2013; Janssen et al., 2016) and participants who receive cognitive behavioral therapy (CBT) treatment (Aderka et al., 2012; Tang et al., 1999) show sudden gains. Ascertaining if a treatment comprising both sauna sessions and CBT sessions is feasible and tolerable will allow for further research of this integrative mind-body treatment as a potentially effective and disseminable treatment for clinical depression.
STUDY DESIGN	Randomized, blinded pilot trial

PRIMARY OBJECTIVE	Pilot RCT procedures: We will conduct a pilot trial ($N=30$) to test the feasibility and acceptability of recruitment, retention, and randomization procedures in preparation for a larger efficacy trial of WBH+CBT. We will randomize participants with clinical depression to receive 8 weekly CBT + 4 biweekly active sauna sessions (refined during Aim 1) or 8 weekly CBT + 4 biweekly sham sauna sessions. After the first half of enrollment ($n=15$) is complete, we will use participant and staff feedback to refine procedures for the remaining enrollment (we will submit any refinements or changes to the treatment to the UCSF IRB approval before implementing them).
SECONDARY OBJECTIVES	To pilot test the feasibility of all assessment procedures in anticipation of a larger trial.
NUMBER OF PARTICIPANTS	30

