PRIMARY ENDPOINT	Primary outcomes. The primary endpoint is study acceptability, as indexed by participant-reported net-promoter scores, which will range from 0 (would not recommend) to 10 (would definitely recommend).
SECONDARY ENDPOINTS	Secondary outcomes. We will assess pre-post intervention changes in: Beck Depression Inventory (BDI-II), Patient-Reported Outcome Measurement System (PROMIS) Depression, PROMIS Anxiety, and the Hamilton Depression Rating Scale (HAMD-6).
OTHER EVALUATIONS	N/A
SAFETY EVALUATIONS	Incidence of unexpected adverse events. We will monitor participants for unexpected adverse events and serious adverse events during and following the sauna sessions.
PLANNED INTERIM ANALYSES	Due to the current study design and safety profile of this test product (portable sauna dome – one person) and cognitive behavioral therapy (CBT; a standard depression psychotherapy treatment), we do not plan any interim analyses.
STATISTICS Primary Analysis Plan	
Primary outcome: We assessed study acceptability by computing means and standard deviations of participant-reported net-promoter scores, which will range from 0 (would not recommend) to 10 (would definitely recommend).
 
Note on Original Primary Outcome: Although we collected and reported this outcome, participants noted that they may not have recommended the study as highly to others because antidepressant medication use was an exclusion criteria, and many participants knew that their friends or family members used these medications. Because that awareness may have biased net promotor scores downward, we report an additional acceptability measure.
 
Revised Additional Primary Outcome: A second study acceptability measure asked participants how likely they would be to enroll in the study given their experience in the study, on a scale from 1 (extremely unlikely to enroll) to 5 (extremely likely to enroll). We reported the score mean and standard deviation.
 
Secondary outcomes: We assessed change in scores on the Beck Depression Inventory (BDI-II), Patient-Reported Outcomes Measurement Information Systems (PROMIS) measures, and Hamilton Depression Rating Scale (HAMD-6), using T-Tests, and report the mean changes and associated standard errors. Units for PROMIS measures are T-Score points.

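### The named safety outcome covers only unexpected adverse events, so expected non-serious events have no stated place in any outcome, and no safety summary by arm is stated.

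*Combined protocol and SAP*

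**What the plan says.** The safety plan is a single row, SAFETY EVALUATIONS: "Incidence of unexpected adverse events. We will monitor participants for unexpected adverse events and serious adverse events during and following the sauna sessions". The available text does not define expected or unexpected. The OTHER EVALUATIONS row is marked not applicable. The STATISTICS row covers two acceptability scores and the changes in the symptom scales, and contains no safety analysis.

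The BACKGROUND and RATIONALE sections both give a purpose that includes tolerability: "Ascertaining if a treatment comprising both sauna sessions and CBT sessions is feasible and tolerable" is said to open the way to further research. The PRIMARY OBJECTIVE row is narrower. It is "to test the feasibility and acceptability of recruitment, retention, and randomization procedures", and it adds that after the first 15 participants "we will use participant and staff feedback to refine procedures for the remaining enrollment". The CONTROL PRODUCT row divides participants equally between active and sham sauna, with CBT for everyone.

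**The concern.** A heating treatment can be free of unexpected events and still be hard to bear, because the effects that staff anticipate may be the common ones. Followed to the letter, the plan yields a safety result from which expected non-serious events are absent by definition. A reader of the report could take a low count as a sign that four sessions were well tolerated, when the count was never built to show that.

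The sham arm adds to the point. Both arms receive CBT and attend sauna visits, so a table of events by arm would help separate the effects of heating from background events. The plan does not commit to such a table.

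**Working it through.** **Plan's own figure.** The documents give none for safety. The only precision figure concerns acceptability: 25/30 = 0.833, and 0.833 ± 1.96 × √(0.833 × 0.167 / 30) = 0.833 ± 0.133, or 70.0% to 96.7%. This agrees with the stated 70% to 97% and has no bearing on the safety outcome.

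**Cross-classification.** Reading the safety row literally gives four classes of event:

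| Class | In the named incidence? | Monitored? |
|---|---|---|
| Unexpected, serious | Yes | Yes |
| Unexpected, non-serious | Yes | Yes |
| Expected, serious | No | Yes |
| Expected, non-serious | No | Not stated |

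Only the last class has no stated place at all.

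**Is that class picked up elsewhere?**

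- Primary outcomes: the net-promoter score (0 to 10) and the would-enroll rating (1 to 5) are overall judgements of the study. They also reflect CBT and study burden.
- Secondary outcomes: BDI-II, PROMIS Depression and Anxiety, and HAMD-6 are symptom scales, not event records.
- Visit schedule: questionnaires are completed at every sauna visit, but their content is not stated.
- Midpoint feedback from participants and staff serves to refine procedures. It is not tied to adverse events.

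None of these brings expected non-serious events into a stated outcome.

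**Does the earlier evidence settle tolerability?** The BACKGROUND section says that prior heating "is tolerable by healthy adults and is associated with significant reductions in clinical depression". It then adds: "This prior work administered a single sauna session in a Heckel heating device". That is one session in a different device. The team's own 25-person pilot is summarized by saying that the commercial sauna "can achieve a core temperature of 101.3 °F without serious adverse events", which is silent on non-serious events. The trial's regimen is "4 biweekly active sauna sessions (refined during Aim 1"; what Aim 1 measured is not in these documents.

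**Exposure.** Participants per arm: 30 × 50% = 15. Planned sauna sessions per arm: 15 × 4 = 60, so 120 in total. This assumes full enrollment, an exact half split and full attendance.

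**Number left out.** This would be the exposure multiplied by the rate of expected non-serious events. No such rate is given, so the number cannot be computed.

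**The case against.** The best case for the plan has five parts.

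1. *Tolerability is not a listed objective.* This stands. The objectives concern trial and assessment procedures, and the primary endpoint is acceptability. A reader might infer that a stated objective goes unmeasured; the documents do not support that. The gap lies between the rationale and the outcomes.

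2. *Relevant evidence is collected.* This stands in part. Willingness to enroll again, given by people scheduled for four sessions, does speak to tolerability, as do retention and feedback. They do so indirectly and do not describe events.

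3. *Much is out of view.* Expected risks may be listed in consent pages that are not in the available text, the sauna questionnaires may ask about symptoms, and Aim 1 may have produced tolerability data. A reader might infer that expected events were ignored or went unrecorded. The documents do not show this: naming one safety outcome does not prove that nothing else was written down. Even so, a list of expected risks would only define the excluded class. It would not bring that class into the outcome.

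4. *The plan states no by-arm analysis for anything.* This is true. Acceptability is a mean and standard deviation, and the symptom scales get t-tests on change. The silence on arms is therefore not peculiar to safety, and the row's heading refers to the primary analysis. What remains is that no safety summary of any kind is stated.

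5. *The sample is too small to compare event rates.* This also stands, and is why the table should be descriptive. Small-sample imprecision does not measure this gap, because it would remain after the change.

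**Conclusion.** The point holds as a cheap improvement. The plan sets a rule that leaves expected non-serious events out of the only named safety outcome, and nothing else in the text brings them in or commits to a summary by arm. The count of unexpected events is correct for what it names, but alone it cannot show how well repeated sessions were tolerated.

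No primary or secondary result changes. The size of the omission is unknown; only the planned exposure (60 sessions per arm) can be stated. The conclusion rests on a literal reading of the safety row and on the absence of any linked definition or event table in the available text. It makes no claim about what was recorded in practice, or about whether the sessions were well or badly tolerated.

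**What to change.** Change the safety outcome to the incidence of all adverse events, expected or not and serious or not, and keep expectedness and seriousness as descriptors of each event. Define expected in the safety row, or cross-refer to the list if one exists elsewhere. Add to the statistics section a descriptive table, active against sham, of the participants with at least one event and the number of events, without a test.

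The statistics section speaks of the primary outcome as already collected and reported, so collection may be complete. In that case the change is one of reporting: tabulate every recorded event by arm and state whether expected non-serious events were captured. If they were not, state that the count of unexpected events is not evidence of tolerability. Events that were never recorded cannot be recovered.

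The cost is a slightly longer event record if collection is open, or one extra table and a sentence on capture if it is closed. The reported event rate may be higher if expected events were captured; it need not change if none occurred or none were recorded. The sample size is unaffected.

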PARTICIPANT SELECTION CRITERIA	
Inclusion Criteria:
 
 1. Age of at least 18 years old 2. Current major depressive episode of at least 2 weeks duration as assessed by the Structured Clinical Interview for DSM-5 (SCID) and a Beck Depression Inventory-II (BDI-II) score ≥ 21 at screening 3. Able to understand the nature of the study and able to provide written informed consent prior to conduct of any study procedures 4. Must have smartphone onto which they can download an app from Apple App or Google Play stores 5. Ability to lie supine (on back) for 2 hours (required for sauna sessions) 6. Must be fully vaccinated against COVID-19 
Exclusion Criteria:
 
 1. $>30\%$ reduction in BDI-II score between Screen #1 and Screen #2 (conducted ~ 1 week after Screen #1). 2. Suicide attempt in the past 12 months defined using the SAMHSA suicidality question during the clinician-administered interview or active suicidal ideation as indexed by a score of 3 on the BDI-II suicidality item during the clinician-administered interview. 3. Any of the following medical conditions: cardiovascular disease (other than controlled hypertension), seizure disorder, history of cerebrovascular accident (CVA) or other serious neurological condition (e.g. Parkinson's disease, multiple sclerosis, or dementia), current neoplasia, any active enclosed infection (e.g. dental abscess, joint infection), hemophilia or other cause for excessive bleeding (e.g. platelet disorder), or other medical

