	
condition that in the opinion of investigators may increase the risk of WBH
 
 4. Comorbid psychiatric conditions or history of comorbid psychiatric conditions that might better explain depressive symptoms, including schizophrenia, schizoaffective disorder, Bipolar Disorder I, Obsessive Compulsive Disorder, Anorexia Nervosa, Bulimia Nervosa, Alcohol Dependence, or Drug Dependence 5. Known hypersensitivity to hyperthermia and/or infrared exposure 6. Inability to fit into the sauna device 7. Breast implants 8. Pregnancy, active lactation or intention to become pregnant during the study period 9. Use of any medication that might impact thermoregulatory capacity, including: 
 • diuretics, barbiturates • beta-blockers • antipsychotic agents • anti-cholinergic agents or chronic use of antihistamines • aspirin (other than low-dose ASA for prophylactic purposes) • medication prescribed for the treatment of depression (antidepressant medication [ADM]) including but not limited to: selective serotonin reuptake inhibitors [SSRIs], Serotonin and norepinephrine reuptake inhibitors [SNRIs], Monoamine oxidase inhibitors [MAOIs], Tricyclics [TCAs], and atypical antipsychotic and antidepressant medications (participants must have been free of these medications for at least 4 weeks) • antibiotics (past 14 days), pain medication (opioids) due to procedure, e.g., dental procedure (past 14 days), Emergency contraception pill (past 14 days) • any other medication that in the judgment of the PI would increase risk of study participation or introduce excessive variance into physiological or behavioral responses to WBH • recent use (multiple consecutive doses) of: non-steroidal anti-inflammatory drugs (NSAIDs), systemic corticosteroids, cytokine antagonists 10. Regular use of any nicotine products, including cigarettes, vapes, chewing tobacco, or other forms of nicotine (if use is not regular, must be willing to refrain for 24 hours before and 24 hours after sauna session) 11. Unwilling to refrain from using marijuana products and alcohol for the 24 hours before and 24 hours after sauna sessions

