	
12. Unwilling to refrain from heavy exercise on the day of sauna sessions
 
13. Unwilling to refrain from engaging with sauna, hot yoga, cold plunges, cryotherapy, and hot tub/jacuzzi outside of study (prospective participant must not have engaged with any of these activities for 30 days prior to their baseline study visit).
 
14. Has begun new psychotherapy treatment in the prior 6 weeks
 
*Note: All medications reported by potential subjects will be reviewed by medical monitor [name]. If the medication is determined to not have meaningful impacts on bodily thermoregulatory processes and to not interact with whole body heating, the subject may participate.

TEST PRODUCT, DOSE, AND ROUTE OF ADMINISTRATION	Portable Sauna Dome – One Person Supine sauna device, head out, body inside of sauna Sauna session approx. 80 – 140 minutes, maximum 140 minutes Manufactured by Clearlight Infrared
CONTROL PRODUCT, DOSE AND ROUTE OF ADMINISTRATION	All participants receive cognitive behavioral therapy (CBT), and 50% of participants receive active sauna sessions while 50% receive sham sauna sessions (the test product treatment listed above, Portable Sauna Dome)
DURATION OF PARTICIPANT PARTICIPATION AND DURATION OF STUDY	
This is a single-center, two-arm, randomized experimental study that will include 30 participants. Participants will be in the study for approximately 10 weeks. Total time involved will be approximately ~34 hours:
 
 • E-Screen: Web-based eligibility screen for self-report eligibility criteria 
 ○ ~10 minutes • Phone Screen: Phone call to review eligibility, verify shipping address for Oura ring sizing kit and schedule baseline study visits 
 ○ ~25 minutes • In-Person Screen / Baseline Visit: Participant to complete screening procedures, provide informed written consent and receive bill of rights, download Oura ring app, complete self-report questionnaires, anthropometric assessments, schedule study visits. Randomization to receive either active sauna sessions or sham sauna sessions. 
 ○ ~220 minutes • Weekly depression survey: Web-based surveys assessing depression symptoms on Mondays. 
 ○ ~ 10 minutes each

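### Safety is measured by unexpected adverse events, with monitoring adding only serious ones, so non-serious events judged expected drop out of the tolerability record in both arms

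*Combined protocol and SAP*

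**What the plan says.** The safety plan is two sentences in the Safety Evaluations row. The first names the measure: "Incidence of unexpected adverse events". The second describes surveillance: "We will monitor participants for unexpected adverse events and serious adverse events during and following the sauna sessions". The Other Evaluations row is marked not applicable, and the Statistics row covers the primary and secondary outcomes only, with no safety summary.

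Suicidality appears once, in exclusion criterion 2. That criterion bars a suicide attempt in the past 12 months, or "active suicidal ideation as indexed by a score of 3 on the BDI-II suicidality item during the clinician-administered interview". Scores of 1 or 2 do not bar entry. After baseline the BDI-II is a secondary endpoint, assessed as pre-post change. The Statistics row says the analysis will use t-tests "and report the mean changes and associated standard errors". No section gives the suicidality item a safety use after entry.

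The Rationale says the study is to establish whether sauna plus CBT is feasible and can be tolerated, and the Primary Objective places it ahead of a larger efficacy trial.

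**The concern.** Tolerability is largely a matter of non-serious effects that could be foreseen, here from sauna sessions lasting up to 140 minutes. That is the class of event the safety wording leaves out. A short synopsis can be silent on a point without harm, but this text is not silent: it restricts the count by expectedness. The documents available here list no expected events, so what gets counted depends on a judgement with no written basis in them.

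The Background describes the earlier pilot of 25 participants only as free of serious adverse events, so it does not supply the missing record. The larger trial would then be planned without a count of minor, foreseeable events from either study, and the sham arm's value as a comparison for those events would be lost.

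On suicidality, the sponsor treats it as a risk at entry. Participants have a current major depressive episode with a BDI-II of at least 21, and for antidepressants "participants must have been free of these medications for at least 4 weeks". It would be natural to follow the same item afterwards for safety, and the plan does not say that this is done.

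**Working it through.** **What is counted.** Cross the two attributes used in the Safety Evaluations row:

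| | Unexpected | Expected |
|---|---|---|
| Serious | measure and monitoring | monitoring only |
| Non-serious | measure and monitoring | neither |

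The lower right cell is the gap. No other section fills it.

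**The plan's own figure.** The plan gives no safety figure. Its one computed figure is the acceptability interval in Rationale for Number of Participants, and it reproduces: 25/30 = 0.833; 0.833 ± 1.96 × √(0.833 × 0.167 / 30) gives 0.700 to 0.967, the stated 70% to 97%. It does not bear on this point.

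**Effect of one omitted participant.** Inputs: 30 participants, allocated 50:50 (Control Product row), so 15 per arm. One participant is 1/15 = 6.7 percentage points. Exact (Clopper-Pearson) 95% intervals:

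- 0/15: 0 to 21.8%
- 1/15: 0.2 to 31.9%
- 2/15: 1.7 to 40.5%

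If the only events in an arm were non-serious and expected, a true 1/15 or 2/15 would be reported as 0/15.

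**How likely such an omission is.** The documents give no rate, so the per-participant risk p of a non-serious expected event is assumed. The chance of at least one affected participant in an arm is 1 − (1 − p)^15, and the expected number is 15p:

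| Assumed p | Chance of at least one | Expected number per arm |
|---|---|---|
| 5% | 54% | 0.75 |
| 10% | 79% | 1.5 |
| 20% | 96% | 3.0 |

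These assumed rates refer to any non-serious expected event, not to suicidal ideation.

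**Whether the planned BDI-II analysis would show a change in suicidality.** A rise of 1, 2 or 3 points on the item in one of 15 participants moves the arm's mean change by 1/15 = 0.07, 2/15 = 0.13 or 3/15 = 0.20 points. A mean change with its standard error cannot reveal one participant's rise on one item.

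**The case against.** The strongest reply is that an event missing from one incidence figure has not gone unseen. Participants attend eight in-person CBT visits with self-report measures, four sauna visits with questionnaires, and a closeout visit with a clinician-administered assessment, and they complete weekly depression surveys. Staff may have recorded every event. This stands as a limit on the point: the gap is in the stated safety record, not shown to be in clinical care. No section says that those contacts feed an adverse-event record, however, and if they did, reporting the result costs only a table.

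Consent pages are not part of the text reviewed, and expected risks may be listed there. That is also fair. Such a list would define which events are excluded; it would not bring them into the count.

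The numbers above hold for any event in any arm of 15, and the rates are assumed. This is correct. They show how sensitive a small arm is, not how many events were missed.

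Two stronger readings are tempting and are not supported:

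- A reader might infer that worsening suicidal ideation would be classed as expected and so go uncounted. No section says so. A score of 3 at interview bars entry, so a later 3 might well be judged unexpected, and a suicide attempt could be captured as serious. Being free of antidepressants is an eligibility condition; nothing says anyone was withdrawn from them for the study. A one-point rise on a single item may be noise.
- A reader might infer that the time between randomization at the baseline visit and Sauna Visit 1 is unmonitored, because the monitoring sentence refers to the sauna sessions. The incidence sentence has no time window, so the documents do not establish that gap.

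Finally, the Statistics row is largely in the past tense and says of the net-promoter score: "Although we collected and reported this outcome". Collection is probably over, which limits what can still be changed.

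**Conclusion.** The point holds in a limited form. By its own wording the plan leaves non-serious events judged expected out of the safety measure and the monitoring sentence, in both arms, although tolerability is part of what the study is for. It also leaves post-baseline suicidality unnamed as a safety measure while collecting the scale that contains the item.

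The number of events affected cannot be stated from the documents. The firm quantity is 6.7 percentage points per omitted participant in an arm of 15; the chances of at least one omission rest on the assumed 5% to 20% range. By-arm counts at this size are description, not a test.

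The conclusion assumes that the wording was followed as written. If staff recorded everything, only the reporting is incomplete. The acceptability outcome, sample size and precision statement are untouched, so the priority is low.

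**What to change.** In Safety Evaluations, replace the restriction to unexpected events with all adverse events and serious adverse events, regardless of expectedness, from consent to the Closeout Visit. In Statistics, add a sentence stating that participants with at least one event will be reported by arm, with exact 95% intervals, as description only.

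Add a descriptive by-arm listing of BDI-II suicidality item scores at the time points collected, flagging any post-baseline score of 3 and any suicide attempt. Do not class every one-point rise as an adverse event. The documents confirm the BDI-II only as a pre-post measure; whether it was also used in the weekly surveys or at CBT visits is not stated. The listing assumes that item-level scores were kept.

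If follow-up is complete, report by arm every event already on record, state that unrecorded non-serious expected events cannot be recovered, and carry the revised wording into the larger trial. If any follow-up continues, the investigators should define the clinical response to a flagged score.

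The cost is a reworded paragraph, a sentence in Statistics, and a short table and listing from data already held. The downside is that reported adverse-event counts will be higher.

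### A 1–5 likelihood-of-enrolling item is given primary rank after net-promoter scores were in hand, while the endpoint row and the sample-size rationale name only the net-promoter score

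*Combined protocol and SAP*

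**What the plan says.** All the text at issue is in the combined protocol and SAP.

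- The PRIMARY ENDPOINT row names one measure: "The primary endpoint is study acceptability, as indexed by participant-reported net-promoter scores", on a 0–10 scale.
- The first paragraph of the Primary Analysis Plan agrees, and gives the analysis: "We assessed study acceptability by computing means and standard deviations of participant-reported net-promoter scores".
- The next paragraph is headed "Note on Original Primary Outcome". It reads in part: "Although we collected and reported this outcome, participants noted that they may not have recommended the study as highly to others". The reason given is that antidepressant use was an exclusion and many participants knew friends or relatives who took such drugs. It concludes: "Because that awareness may have biased net promotor scores downward, we report an additional acceptability measure".
- The paragraph after that is headed "Revised Additional Primary Outcome". It says: "A second study acceptability measure asked participants how likely they would be to enroll in the study given their experience in the study". Answers run between 1 and 5. The paragraph closes: "We reported the score mean and standard deviation".
- The Rationale for Number of Participants again names only the net-promoter score as the primary endpoint.

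**The concern.** The current plan gives two answers to the question of what is primary. One section ranks the 1–5 item as a primary outcome; the endpoint row and the sample-size rationale do not mention it. The text at issue is the operative analysis plan, not an amendment log.

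The order of events matters more than the mismatch. A second measure was raised to primary rank because the first was thought to read too low. That is a data-informed change of primary outcome, and its reason works in one direction only. The plan does not say how many participants made the remark or how far scores might have shifted.

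Acceptability is the named primary endpoint of a pilot meant to prepare a larger efficacy trial. With two measures called primary and no rule for which carries the conclusion, the acceptability statement could rest on the one promoted later.

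**Working it through.** This is a question of consistency and timing, so the check is mainly a comparison of the text. The plan's one related figure comes first.

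**1. The plan's own figure.** The sample-size rationale supposes that 25 of 30 participants rate the study above 7 and uses the normal approximation:

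- p = 25/30 = 0.8333
- SE = √(0.8333 × 0.1667 / 30) = 0.0680
- 1.96 × 0.0680 = 0.1334
- 95% CI = 0.8333 ± 0.1334 = 70.0% to 96.7%

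This matches the stated 70% to 97%. The figure is not in dispute, and nothing below changes it.

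**2. Which measure is primary, by section.**

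| Section | Net-promoter score (0–10) | Likelihood of enrolling (1–5) |
|---|---|---|
| PRIMARY ENDPOINT row | primary | not mentioned |
| Primary Analysis Plan | primary, then called original | also primary, called revised and additional |
| Rationale for Number of Participants | primary | not mentioned |

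The endpoint row and the rationale therefore conflict with the heading "Revised Additional Primary Outcome".

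**3. When the rank was given.** Three features of the wording bear on this:

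- One measure is called original and the other revised.
- The note on the net-promoter score says it had already been collected and reported.
- The reason for the addition is what participants said about recommending the study, so it could not have been given before participants had commented.

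Together these place the primary rank of the 1–5 item after net-promoter data existed.

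**4. What the wording leaves open.** The documents do not say when the 1–5 item was first asked, whether net-promoter scores had been seen by then, or how many participants answered it. The Closeout Visit entry mentions questionnaires in general and names neither measure, so it does not settle the matter.

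**5. Effect on the analysis.** Both measures are summarised by mean and standard deviation, with no test and no success threshold for either. No error rate can be inflated and no estimate moves. The documents give no results, so the size of any shift in emphasis cannot be computed.

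**The case against.** The best defence is that nothing is hidden. The plan calls one measure original and the other revised and additional, states why, keeps the net-promoter score first, and says it was reported. The reason also has substance. Recommending a study to others depends partly on whether they could join, and exclusion criterion 9 does bar antidepressant users. A question about the participant's own willingness avoids that difficulty, and both items bear on acceptability. The sample-size rationale is written prospectively, so it would naturally name only the first measure.

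Most of this stands. It shows that the item is a reasonable complement and that the net-promoter score was supplemented, not silently replaced. It does not justify primary rank. Disclosure leaves the heading at odds with the endpoint row and the rationale, and it omits the timing and the number of respondents.

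A reader might infer more than the documents support:

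- **That the 1–5 item was first asked late.** The text shows only that its primary rank came later.
- **That type I error is inflated.** There is no hypothesis test on either measure.
- **That the net-promoter score has planned precision and the 1–5 item has none.** The interval in the rationale is for a proportion rating above 7, while the Primary Analysis Plan analyses the net-promoter score by mean and standard deviation. Neither mean has planned precision, so this does not separate the two measures.

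**Conclusion.** The point holds, at minor-to-moderate weight. The Primary Analysis Plan gives primary rank to a measure that the endpoint row and the sample-size rationale do not name. It does so after net-promoter scores had been collected and reported, on the ground that they may read too low. No estimate, sample size or error rate changes. What changes is which measure may carry the primary acceptability conclusion.

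This rests on reading the note's past tense at face value. If it was a later write-up of an earlier decision, the stated reason still depends on participants' comments, so the rank cannot predate all participant feedback. The documents do not show that the sponsor chose the more favourable measure or that any report led with it. The concern is that the plan leaves this open.

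**What to change.** Make these changes in the Primary Analysis Plan:

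- Keep the net-promoter score as the sole primary outcome.
- Relabel the 1–5 item as a supplementary (post hoc) acceptability measure.
- Report it beside the net-promoter result, with its number of respondents, when it was introduced, and whether net-promoter scores had been seen by then.
- Use the antidepressant-exclusion explanation only to interpret the net-promoter result.

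The cost is one heading and two or three sentences, with the same label carried into any results already reported. No new data are needed. The downside is that the 1–5 item can no longer carry the primary claim.
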